## 4 Administration of Study Treatment

Potential first-time donors will be asked if they are interested in participating in a study of the prevalence of ID and IDA and the impact of iron supplementation on haemoglobin levels and repeat donation. Those who express interest, consent to the study, and are eligible will be asked to return within 3 weeks. During this 3-week period a FBC, a peripheral blood film analysis, and a plasma ferritin measurement will be conducted, and participants will be classified as iron supplement participants (e.g., anaemic, ID, IDA) or otherwise (which we refer to as controls in this protocol).

Those found to be anaemic, ID or IDA will receive oral iron supplementation and nutritional counselling. The oral iron supplements will be ferrous sulphate 200mg (65mg Elemental iron). The iron supplements are already available at the Korle-Bu Teaching Hospital Pharmacy. The study principal investigators and study pharmacist will ensure the medicine is stored properly and dispensed only when needed for study participants. The following will be monitored and completed on a periodic basis to ensure the medicine is within study guidelines, pharmaceutical compliance, and manufacturer guidelines:

Drug Accountability Record.

Iron supplement Safety and Handling Sheet.

Controls will not be given iron supplementation at enrolment but will receive the standard practice of nutritional counselling for blood donors. If someone not given iron supplements at enrolment is found to be anaemic, ID or IDA at a follow-up visit that individual will receive iron supplements.

All study participants will have nutritional counselling, dietary advice, and for those

receiving iron, the need for iron therapy to be used consistently 3 days a week.

## 5 Safety Assessment

### Definitions

#### **Adverse Event (AE)**

An AE is any untoward or unfavourable medical occurrence in a study participant, including any abnormal sign (e.g., abnormal physical exam or laboratory finding), symptom, or disease, temporally associated with their participation in research. Only AEs potentially related to iron supplementation will be recorded as AEs.

At each follow-up visit all participants will be asked if they have experienced each item from a list of common adverse reactions to iron supplementation. Furthermore, the occurrence of additional AEs will be sought by non-directive questioning of the study participant at each visit during the study. AEs also may be detected when they are volunteered by the study participants during or between visits or through physical examination findings, laboratory test findings, or other assessments.

Adverse events will be recorded in the Adverse Events electronic case report form (eCRF) under the signs, symptoms, or diagnosis associated with them, accompanied by the following information (as far as possible):

AEs will be assessed.

Its relationship to the study treatment.

Its duration (start and end dates) or if the event is ongoing, an outcome of not recovered/not resolved must be reported.

The grade of the AE.

Whether it constitutes a SAE.

Action taken regarding with study treatment.

All AEs will be treated appropriately. Treatment may include one or more of the following:

- Dose not changed.
- Dose Reduced/increased.
- Drug interrupted/withdrawn.
- Its outcome (i.e., recovery status or whether it was fatal).

If the event worsens the event will be reported a second time in the eCRF noting the start date when the event worsens. For grade 3 and 4 AEs only, if improvement to a lower grade is determined a new entry for this event will be reported in the eCRF noting the start date when the event improved from having been grade 3 or 4.

Adverse events (including lab abnormalities that constitute AEs) will be described using a diagnosis whenever possible, rather than individual underlying signs and symptoms.

Once an AE is detected, it will be followed until its resolution or the end of follow-up and an assessment will be made at each visit (or more frequently, if necessary) of any changes in severity, the suspected relationship to the interventions required to treat it, and the outcome. If an AE has not resolved by the end of follow-up for a participant, the outcome of the AE will be recorded as unknown.

Common adverse reactions to iron supplementation are minor and include:

- Unpleasant taste.
- Constipation.
- Dark stools.
- Nausea.
- Vomiting.
- Abdominal pain.
- Diarrhea.

Abnormal laboratory values or test results constitute AEs only if they fulfil at least one of the following criteria:

- They induce clinical signs or symptoms.
- They are considered clinically significant.
- They require therapy.

Clinically significant abnormal laboratory values or test results will be identified through a review of values outside of normal ranges/clinically notable ranges, clinically significant changes from screening or the previous visit.

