## **Objectives**

### **Primary Objectives**

The primary objective of the Iron Supplementation Trial is to determine the potential for an iron supplementation strategy to increase blood donations in Ghana. To determine this potential, the study will investigate the feasibility and acceptability of this intervention along with key return blood donation measures among first-time blood donors found to have low haemoglobin or found to have IDA or be ID within the catchment areas of the SZBC. These aspects of the potential for this intervention will be

operationalized as follows:

- **Feasibility** of recruitment, enrolment, retention, and adherence will be evaluated with a target retention rate > 90% of all participants recruited completing the trial. If we are unable to achieve this target, alternative strategies will be considered for the UH3 phase.
- **Acceptability** will involve establishing the safety profile of 3 times weekly low dose ferrous sulphate (65mg elemental iron) supplements among those assigned to iron supplementation at enrolment. This safety profile will be established by comparison to a similar group of participants who do not receive iron supplementation. Participant and key informant views and perspectives of barriers and recommendations for using iron supplementation and nutritional counselling to increase the blood donor pool will also be investigated with participant questionnaires. In addition, FGDs and key informant interviews will provide critical insights into the acceptability of this intervention.
- **Key blood donation measures** include haemoglobin levels at 4 months, the change in haemoglobin concentration, ferritin levels at 4 months, the proportion of participants with corrected ID, the proportion of participants who return to the blood centre to donate blood and the proportion of returners who are able to successfully donate (not deferred). In addition, the incidence of ID and IDA among blood donors will be determined among those who consent to the Iron Supplementation Trial at screening.

To achieve this objective, a pilot parallel groups trial will be conducted for one year. This allows for enrolment over a maximum of 6 months and 6 months of follow-up for the last individual enrolled. The follow-up period incorporates 4 months of the iron supplementation intervention.

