### 2.2 Randomization

There is no randomization in the cross-sectional component. In the parallel groups' component, the 2 groups will be determined based on the need for iron supplementation, so the treatment is not assigned by randomization.

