### 2.3 Blinding

The participants and the investigators are not blinded.

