### ***Causality***

Causality refers to the likelihood that the event is related to the study intervention. It will be assessed for SAEs and UPs.

The causality assessment is based on available information at the time of the assessment of the event. The investigator may revise these assessments as additional information becomes available.

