### Secondary analyses of secondary outcomes related to safety and feasibility

To maximize the power to detect an association between group membership and safety outcomes, a composite of grade 3 and 4 AEs, SAEs, gastro-intestinal problems, malaria, and bacterial infections will be constructed and compared between the groups.

The frequency of this composite will be compared between groups using Fisher's exact test. Furthermore, logistic regression models will be fit with group membership, sex, and age as covariates and the odds ratio associated with group membership will be estimated along with a 95% confidence interval. These models will be parameterized so that an OR greater than 1 indicates that the intervention group has a higher incidence of negative outcomes. Components of the composite will also be investigated using a similar approach.

The questions about known side effects to iron supplementation ask: Has the participant experienced any of the following since the last visit (mark all that apply)?

- Unpleasant taste.
- Constipation.
- Dark tools.
- Nausea.
- Vomiting.
- Abdominal pain.
- Diarrhea.
- Other; specify.

The incidence of each of these outcomes over follow-up will be computed and logistic regression models will examine the impact of group membership, sex, and age on these outcomes. The odds ratio and a 95% confidence interval for the group membership variable will be used to summarize the association. Models which look at the incidence of any of these outcomes will also be examined and an odds ratio and 95% confidence interval will be used to summarize the relationship.

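### AE recording is limited to events potentially related to iron, with no rule for participants not taking iron, so between-group comparisons drawn from the AE eCRF may under-count control events

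*SAP*

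**What the plan says.** **Recording rule.** SAP section 5, Adverse Event, states: "Only AEs potentially related to iron supplementation will be recorded as AEs". The Protocol's Adverse Event definition has the same sentence. In both documents, Schedule for Data Collection and Reporting of Specific Events also describes safety recording in terms of iron-related AEs, and Severity limits grading to them.

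**Design.** SAP 2.3: "The participants and the investigators are not blinded". SAP 2.2 says that the groups follow from need for iron, "so the treatment is not assigned by randomization". SAP section 4: "Controls will not be given iron supplementation at enrolment". A control found anaemic or iron deficient later is treated differently: "that individual will receive iron supplements". SAP 7.2 still counts that person as a control, because groups are defined by assignment at enrolment.

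**Use of the data.** Under Primary Objectives, on acceptability: "This safety profile will be established by comparison to a similar group of participants who do not receive iron supplementation". SAP 7.2.2 lists incidence of grade 3 or 4 AEs as an outcome and says that "a composite of grade 3 and 4 AEs, SAEs, gastro-intestinal problems, malaria, and bacterial infections will be constructed and compared between the groups", by Fisher's exact test and logistic regression, with the components examined similarly. The Protocol's composite does not contain grade 3-4 AEs but compares them between groups separately.

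**Attribution.** Relationship to study treatment is an item on the AE eCRF. The Causality section says of causality: "It will be assessed for SAEs and UPs".

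**The concern.** A between-group comparison needs numerators collected alike in both groups. Here an event enters the AE eCRF only if it might be due to iron, and exposure to iron is what separates the groups. Staff know who takes iron. A member of staff applying the rule to a control not on iron could reasonably conclude that nothing this person reports can be iron-related, and leave it out. The same complaint from a supplemented participant would be entered.

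Acceptability is part of the primary objective and rests partly on this comparison, which also informs planning of the UH3 phase. Under-recording in controls would make iron look more harmful than it is.

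**Working it through.** **1. Which results pass through the rule**

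- *Outside it.* The list of known iron reactions is put to all participants at each follow-up visit. All SAEs are reported. The malaria rapid test is scheduled at every follow-up visit without restriction by arm.
- *Inside it.* The checklist carries no grade, so a non-serious grade 3-4 event can reach the analysis only through the AE eCRF. Events found by open questioning, volunteered reports, examination or laboratory results are also exposed, apart from whatever the checklist's free-text line captures.
- *Unknown.* The source of the gastro-intestinal component (checklist or AE eCRF) is not stated. Nor is the source for bacterial infection, for which the schedule has no test; the Protocol describes cultures only when infection is suspected or they are indicated.

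**2. Arm size for the illustration**

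The plan gives no event rate or power for safety, so I take the arm size from the primary outcome (SAP 2.4): margin 1.0, true difference -0.3, SD 1.89 g/dL, one-sided alpha 0.025, power 85%.

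n per arm = 2 × (1.960 + 1.036)² × 1.89² / (1.0 - 0.3)² = 131, as the plan states. Allowing 10% loss, 131/0.9 = 146 per arm, 292 in total, which also agrees.

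**3. Filtered AEs, with no true difference**

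Assumptions, none from the documents: true rate p is equal in both arms, all iron-arm events are recorded, and a share c of control events is recorded.

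OR = [p/(1-p)] / [cp/(1-cp)]. For p = 0.05 and c = 0.5: (0.05/0.95)/(0.025/0.975) = 2.05.

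Rejection rates are exact for the two-sided 5% Fisher test at 146 per arm.

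| True rate | Expected recorded events, iron v control (c = 0.5) | OR (c = 0.5) | Rejection (c = 0.5) | Rejection (c = 1) |
|---|---|---|---|---|
| 5% | 7.3 v 3.7 | 2.05 | 11.5% | 2.4% |
| 10% | 14.6 v 7.3 | 2.11 | 28.8% | 3.2% |
| 20% | 29.2 v 14.6 | 2.25 | 61.7% | 3.6% |
| 30% | 43.8 v 21.9 | 2.43 | 84.4% | 3.7% |

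With c = 0.75 the OR is 1.35 to 1.48 and rejection 4.1% to 26.3%. With c = 1 the OR is 1.00.

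**4. The composite**

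Assume an unfiltered part with rate u = 20% and an independent filtered part with rate f = 10%.

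- Iron arm: 1 - 0.80 × 0.90 = 0.28.
- Controls, c = 0.5: 1 - 0.80 × 0.95 = 0.24. OR = (0.28/0.72)/(0.24/0.76) = 1.23; rejection 9.7%.
- Controls, c = 0: 0.20. OR = (0.28/0.72)/(0.20/0.80) = 1.56; rejection 31.1%.
- Equal recording: OR 1.00; rejection 3.7%.

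**The case against.** **The rule may be neutral by arm.** The text names no judge and no decision per participant. It could mean that only types of event that iron can cause are recorded, in either group. The separate relationship item supports this, since it would add little if entry already required a verdict on relatedness. On this reading c = 1 and nothing tilts. The reading is possible but not written down. It also fits poorly with open questioning for additional events: no list covers what that may turn up, so someone must decide event by event, knowing the group.

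**Much of the safety data bypasses the rule.** This stands. A reader might infer that the whole safety comparison is biased by construction. The documents do not support that, given the checklist, SAEs and malaria tests. Severe events also overlap with SAEs: the grade 4 definition and the SAE criteria both refer to intervention to prevent serious outcomes. Controls who later start iron can have iron-related events in the ordinary sense.

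**Attribution is not wholly unassessed.** This also stands. The AE eCRF has a relationship field. However, it is completed only for events already entered, and the Causality section mentions only SAEs and UPs, so the two sections need reconciling.

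**Large odds ratios rest on assumption.** A 5% true rate with 50% of iron-arm events and 5% to 25% of control events judged related gives 2.5% against 0.25% to 1.25% recorded, an OR of 10.2 to 2.0. At 146 per arm that is 3.65 against 0.4 to 1.8 events, and even 4 against 0 gives a two-sided Fisher p of about 0.12. The Protocol expects AEs to be infrequent, so an OR of 10 should not be put forward as the likely effect.

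**Conclusion.** The point holds as an undefined recording rule that can under-record control events. It is not an established bias in all safety results. The exposed results are non-serious grade 3-4 AEs, other unsolicited AEs, and any gastro-intestinal or bacterial-infection component taken from the AE eCRF. The SAP composite is exposed in part.

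If relatedness is decided per participant, the direction is towards apparent harm from iron. The size depends on event rates and recording shares that the documents do not give. With half of control events recorded, the illustration gives an OR of about 2.1 to 2.4 for filtered AEs and about 1.2 for the composite. For infrequent events the low end of the rate range is the more relevant: a distorted estimate, with a false significant result in about one trial in nine (11.5% at a 5% rate).

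The sample size is unaffected. Neither document sets a formal stopping rule that such a tilt would trigger. The change is worth making because it removes the problem under either reading of the rule.

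**What to change.** **Preferred.** Record all grade 3-4 AEs and suspected infections in both arms regardless of attribution. Keep the existing relationship field as a descriptor and not as a condition of entry. Amend, in both documents, the Adverse Event definition and Schedule for Data Collection and Reporting of Specific Events. Severity needs the same change, so that grading is not confined to iron-related events. Reconcile the relationship item with the Causality section. Cost: a short Protocol, SAP and eCRF wording change and a few more AE entries in controls.

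**If collection cannot change.** In SAP 7.2.2, restrict the between-group safety comparisons and the composite to events ascertained identically in both arms (checklist, malaria rapid test, SAEs), and list other AEs descriptively. This needs SAP wording only. Its cost is a narrower composite, without non-serious grade 3-4 AEs outside those sources.

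**In either case.** State the data source of each composite component.

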### **Serious Adverse Event (SAE)**

Serious adverse events (SAEs) are defined as the following:

- Death.
- Life-threatening (i.e., an immediate threat to life).
- Hospitalization or prolongation of hospitalization.
- Persistent or significant incapacity or substantial disruption of the ability to conduct normal life functions.
- Congenital abnormalities/birth defects.

Other important medical events that may jeopardize the participant and/or may require intervention to prevent one of the outcomes listed above.

Information about all SAEs will be collected and recorded on the electronic Serious Adverse Event Report Form; all applicable sections of the form will be completed in order to provide a clinically thorough report. The investigator will assess and record the relationship of each SAE to the study intervention, complete the SAE Report Form in English, and submit the completed form within 24 hours to the College of Health Sciences IRB.

All follow-up information for the SAE including information on complications, progression of the initial SAE and recurrent episodes will be reported as follow-up to the original episode within 24 hours of the investigator receiving the follow-up information. An SAE occurring at a different time interval or otherwise considered completely unrelated to a previously reported one will be reported separately as a new event.

Follow-up information will be submitted in the same way as the original SAE Report and will describe whether the event has resolved or continues, if and how it was treated, and whether the study participant continued or withdrew from study participation.

We do not anticipate any SAEs directly related to iron supplementation in this study. However, accidental ingestion of a large amount of oral iron preparation may result in acute iron poisoning which can manifest as severe diarrhoea, acidosis, shock, and death. Study participants will be educated and strict instructions on iron supplementation given and the need to store them away from children. Study pills will be distributed in child-safe containers. The pills will be taken three times weekly, specifically Mondays, Wednesdays and Fridays.

### ***Unanticipated Problems***

An Unanticipated Problem (UP) is any incident, experience or outcome that is:

Unexpected in terms of nature, severity, or frequency in relation to:

- The research risks that are described in the IRB-approved research protocol and informed consent document; Investigator's Brochure (IB) or other study documents.
- The characteristics of the population being studied.
- Possibly, probably, or definitely related to participation in the research.

Places study participants or others at a greater risk of harm (including physical, psychological, economic, or social harm) than was previously known or recognized per the IB.

Furthermore, an UP could be an expected event that occurs at a greater frequency than would be expected based on current knowledge of the disease and treatment under study. The DSMB providing oversight to the study may make such an assessment based on an aggregate analysis of events.

### ***Severity***

The investigator will evaluate all AEs related to iron supplementation with respect to both seriousness (results in outcomes as above) and **severity** (intensity or grade).

The following generic scale will be used:

Grade 1	Symptoms causing no or minimal interference with usual social and functional activities
Grade 2	Symptoms causing greater than minimal interference with usual social and functional activities
Grade 3	Symptoms causing inability to perform usual social and functional activities
Grade 4	Symptoms causing inability to perform basic self-care functions, or medical or operative intervention indicated to prevent permanent impairment, persistent disability, or death
Grade 5	Events resulting in death

### ***Causality***

Causality refers to the likelihood that the event is related to the study intervention. It will be assessed for SAEs and UPs.

The causality assessment is based on available information at the time of the assessment of the event. The investigator may revise these assessments as additional information becomes available.

### **Expectedness**

The expectedness assessment is based on available information at the time of the assessment of the event. The investigator may revise these assessments as additional information becomes available.

### **Schedule for Data Collection and Reporting of Specific Events**

Safety assessments will consist of monitoring and recording all AEs related to iron supplementation. It will also include regular monitoring of laboratory assessments including FBC and plasma ferritin.

### **Halting Enrolment for Safety Reasons**

The study may be discontinued at any time by the IRB, DSMB or National Heart, Lung, and Blood Institute (NHLBI) as part of their duties to ensure that research participants are protected.

## **6 Qualitative Data Analysis**

Qualitative data collection and analysis will proceed simultaneously. In all, ten focus groups of 8-10 participants purposively selected with one group from each blood donation group categories (i) religious organizations, (ii) educational institutions, (iii) corporate institutions, (iv) organized community groups, and (v) walk-in blood donors. The aim of the focus groups is to identify barriers and recommendations for using iron supplementation and nutritional counselling to increase the blood donor pool.

FGDs will be audio recorded with consent from the participants. Information obtained will be transcribed verbatim and translated when appropriate. The qualitative analysis will include: (1) preliminary exploration of the data by reading through the transcripts and writing memos; (2) coding the data by segmenting and labelling the text; (3) using codes to develop themes by aggregating similar codes together; (4) connecting and interrelating themes; (5) constructing a narrative. Data will be coded and analysed for themes using the Qualitative Software and Research Nvivo 1.0 (March 18, 2020).

The qualitative study will be used to guide implementation and evaluation of the larger study at the UH3 phase, including identifying barriers and recommendations for using iron supplementation and nutritional counselling to increase the blood donor pool. Moreover, qualitative findings resulting from focus groups to be conducted at the end of the trial at the UG3 phase and key informant interviews will be used to guide the planning, implementation, and evaluation of the UH3 phase.

